### Eligible patients

The healthcare professionals in general practice identify eligible patients for the project. Identified patients receive oral and written information about the study from the care coordinator. Patients who agree to participate provide informed consent for participation in the study collected by the care coordinator.

### Inclusion criteria:

The study group is patients with complicated multimorbidity in general practice that fulfil the four inclusion criteria:

1. Has more than one of the 3 common chronic diseases (diabetes, chronic obstructive pulmonary, chronic heart conditions) [27].
2. Has been hospitalised, or visited an outpatient clinic due to their chronic diseases during the previous year [17].
3. Take at least five different prescription drugs assessed from the Shared Medicine Card recording (FMK, in Danish “Fælles Medicinkort”) in the general practice [28].
4. The GP or the nurse in the practise recognise the patient as a “demanding” patient with complicated multimorbidity that will benefit from an overview consultation.

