### *Randomization and blinding*

General practices in the designated municipalities are contacted with an invitation to participate in the study. If a general practice agrees to participate in the project, they will receive detailed study information. The 14 participating general practices will be randomised into either the intervention group providing care as described in the CIM2 model or the control group, providing usual care. The general practices will be randomly allocated, at an allocation rate of 1:1, by a computer program. To ensure concealment of allocation, a data manager from another organisation with no interest in the project will provide the information of the randomization to the general practice draw and will be responsible for a randomization list, which will be available to the investigator. Due to the nature of the study, the general practices and the patients cannot be blinded.

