### The intervention elements in the CIM2 model (Figure 2.)

- Training of healthcare professionals during a four-hour one-day course

The training program is developed in collaboration with The Danish College of General Practitioners. Healthcare professionals from general practice, nurses and physiotherapists from the municipalities, and healthcare professionals from the out-patient clinics participate in a training program. Healthcare professionals from general practice will receive training in project content, and methods to recruit and include patients (including informed consent). Further, does the education program offer training in the collection of patient data comprising the use of REDCap software for patient questionnaires.

[figure not shown]
For general practices allocated to the intervention group, the training also includes how to provide medical care for patients with complicated multimorbidity, case-based teaching, patient centred methods, structure and implementation of the extended overview consultation, and development of the care plan. Further, the training cover methods for improving collaboration and integration between general practice, the municipality, and the out-patient clinics using methods known from the national disease management programs.

- The extended overview consultation (in Danish “overblikskonsultation”) in general practice

The patient intervention starts with an extended overview consultation, lasting 45 minutes, with the GP, the patient (and maybe a relative), and the care coordinator. The consultation is based on the guidance for a patient-centred overview status for patients with multimorbidity published by The Danish College of General Practitioners [29]. The aim is to get an overview of the patient’s conditions, problems, and needs. The patient’s goals, preferences, and needs are identified, and treatments of the patient’s various conditions are prioritized. The GP decides who has the treatment responsibility for each condition. The patient’s resources for handling the chronic diseases are elicited, and if the patient is motivated, a referral to a relevant rehabilitation program in the municipality is planned [30]. The individual care plan is developed, covering planned activities in the three sectors that will take place within the 12-month intervention period. The GP will try to reduce the number of outpatient visits in the hospital or replace

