outpatient visits with GP visits if the patient and the specialist agree. The GPs are reimbursed with 1.000 DKK. for the extended overview consultations

Figure 2. Central activities during the implementation and intervention phases of the study “Complex intervention for patients with complicated multimorbidity model version 2 (CIM2)” over time.

- The individual care plan

The individual care plan includes 6 themes: [29] 1) Listing of important diagnoses, 2) Overview of the patient's prescription drugs, 3) Prioritising the patients' treatment goals (using shared decision-making), 4) Development of a coordinated care plan with telephone follow-up and future visits, 5) Plan for potentially reducing the number of visits to hospital out-patient clinic for example by shifting hospital out-patient clinic visits to general practice, and 6) Referral to community-based rehabilitation. The care plan is printed for the patient.

- Care coordinator

General practice coordinates the planned patient care between general practice, the municipality, and the hospital, and follow-up on the execution of planned healthcare activities. The care coordinator function might be undertaken by the GP or the nurse in the practice. The practice plans the division of responsibilities and tasks in the project between the GP and the nurse.

- Follow-up activities

The follow-up activities include telephone calls to the patient by the care coordinator at relevant time intervals according to the severity of conditions and other important factors to follow up on planned activities with the patient. A second extended overview consultation takes place after 12 months.

- Integration of care elements

The individual care plan is shared electronically with the healthcare center in the municipality and with the outpatient clinics using the standard IT-communication tool provided by MedCom and a routinely used national standard in general practice, hospitals, and municipalities.

The GPs and hospitals are offered the opportunity for using cross-sectorial video conferences to plan the patient pathway as described in the OK22. This means that the GP arranges the conference when there is a professional indication for the conference. The GPs' participation in the videoconference is reimbursed.

The health professionals in the municipality provide information to the GP when patients have finished a rehabilitation program.

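### Allocation is concealed only for the draw of practices; if practice staff know their arm when they list and consent patients, the subjective fourth inclusion criterion can be applied differently by arm

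*Protocol*

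**What the plan says.** Under *Randomization and blinding*, 14 general practices are allocated 1:1 by computer. The concealment measure concerns that draw: "To ensure concealment of allocation, a data manager from another organisation with no interest in the project will provide the information of the randomization". That person also keeps the list. The same section states that "the general practices and the patients cannot be blinded".

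Under *Eligible patients*, "The healthcare professionals in general practice identify eligible patients for the project", and the care coordinator informs them and takes consent. The intervention section adds: "The care coordinator function might be undertaken by the GP or the nurse in the practice".

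Under *Inclusion criteria* all four criteria must be met. The first three (diagnoses, hospital contact in the previous year, at least five prescription drugs) can be checked in records. The fourth requires the GP or nurse to "recognise the patient as a “demanding” patient with complicated multimorbidity that will benefit from an overview consultation". The extended overview consultation opens the patient intervention. *The control group – usual care* describes usual care plus a routine conversation with the nurse, and no overview consultation.

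On timing, the first intervention element is "Training of healthcare professionals during a four-hour one-day course". General practice staff receive "training in project content, and methods to recruit and include patients (including informed consent"), and then: "For general practices allocated to the intervention group, the training also includes how to provide medical care for patients with complicated multimorbidity".

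**The concern.** In a cluster trial, concealing the draw of clusters does not protect the selection of patients if that selection comes later and is made by people who know the cluster's arm. Here the selectors and consent-takers are staff of the randomised practice, and no readable part of the protocol withholds the arm from them.

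Criterion 4 is the exposed point. For staff in an intervention practice it asks who would gain from a consultation they are about to deliver. For staff in a control practice it asks about one the protocol does not provide in their arm. The same words can therefore lead to different patients.

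Two things are at stake. The first is the comparison of PACIC, EQ-5D-5L and MTBQ between arms. The second is what the pilot hands to MM600: recruitment counts, the judgement whether the recruited patients are the right ones, and whether 25 per practice is realistic. The recruitment procedure itself could also be carried forward. No distortion of the ICC or variance estimates is claimed.

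**Working it through.** **Order of events.** The readable text does not state the order of disclosure, listing and consent. The training description is the best evidence. Recruitment and consent methods are taught in the same four-hour, one-day course that carries extra content for practices already allocated to the intervention. Staff who learn to recruit on that day would know their arm unless they recruit before attending. This is an inference, not a statement in the protocol.

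**Possible size.** The protocol gives no figure for selection bias, so there is none to reproduce. The following is an illustration. From the power section: 25 patients per practice, target difference 0.36, total variance 1 (so SD 1), ICC up to 0.1. Assumed: in one arm, k of 25 patients per practice are chosen differently and differ by d on mean PACIC.

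Shift in the unadjusted arm contrast = (k/25) × d

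| k | d | Shift | Shift / 0.36 |
|---|---|---|---|
| 2 | 0.25 | 0.02 | 6% |
| 5 | 0.25 | 0.05 | 14% |
| 5 | 0.5 | 0.10 | 28% |
| 5 | 1.0 | 0.20 | 56% |
| 10 | 1.0 | 0.40 | 111% |

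**Would a baseline check catch it?** PACIC is collected at baseline, so one could compare the arms then. Assume baseline PACIC has the variance and ICC used in the power section, with 7 practices of 25 per arm.

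SE = √[(2/7) × (ICC + (1 − ICC)/25)]

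- ICC 0.1: √[(2/7) × 0.136] = 0.197
- ICC 0.05: √[(2/7) × 0.088] = 0.159
- ICC 0: √[(2/7) × 0.040] = 0.107

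With 12 degrees of freedom the two-sided 5% critical value is 2.179. Power comes from the noncentral t distribution with noncentrality shift/SE.

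| ICC | 95% half-width | Power, shift 0.10 | Power, shift 0.20 |
|---|---|---|---|
| 0.1 | 0.43 | 7.5% | 15.5% |
| 0.05 | 0.35 | 9.0% | 21.3% |
| 0 | 0.23 | 13.9% | 40.6% |

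The half-widths are ordinary sampling error. They do not measure the bias; they show only that this check is weak.

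**Checks the protocol does plan.** Register data will be used to compare the groups on sociodemographics, chronic conditions and medicine, and clinicians will review the characteristics of recruited patients. Both follow recruitment and rest on recorded characteristics. Neither prevents selection on an unrecorded clinical judgement.

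**The case against.** The strongest reply is that the order is unknown rather than wrong. The timeline, the flow diagram and the figure of activities over time are not shown in the text available, and any of them may place listing before disclosure. The training text does not say that recruitment follows the course, and the statement that practices cannot be blinded may concern delivery of care only. This stands as a limit, and it is why the concern is conditional.

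Second, criterion 4 has the same wording for both arms and can be read as a need for a consultation of the kind described in national guidance. That is a possible reading. It does not remove the incentive to read the criterion differently once the arm is known.

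Third, none of the pilot's three objectives is an estimate of effect, and studying recruitment is part of its purpose. This lowers the stakes for the outcome comparison. It does not help the second objective: arm-dependent selection distorts the recruitment findings, and without a log by arm it would be hard to recognise.

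Fourth, k and d are assumed and span a wide range, adjustment for baseline PACIC would normally remove part of a shift, and the protocol does not propose the baseline test used above. All true. The arithmetic is illustrative, and the case rests on the text.

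Finally, one sentence giving the order might suffice. It would if the order is already safe, but not if disclosure comes first.

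**Conclusion.** The concern holds in its conditional form and should be fixed; confidence is medium. The protocol conceals the draw of practices but describes no protection for the selection of patients within them. Its one subjective criterion is tied to the consultation that only the intervention arm is described as receiving. The text points towards the arm being known before recruitment without saying so, and the missing figures could show otherwise.

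The size cannot be determined from the documents. A shift of 0.05 to 0.20 on PACIC (14% to 56% of 0.36) follows if a fifth of patients per practice in one arm are chosen differently and differ by 0.25 to 1.0. A baseline comparison of 7 against 7 practices would miss a 0.10 shift at least 86% of the time at any ICC from 0 to 0.1. Criteria 1 to 3 are less exposed.

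**What to change.** - In *Randomization and blinding* and *Eligible patients*, state that each practice draws candidates from its records on criteria 1 to 3, applies criterion 4 and locks the list before the data manager discloses the allocation. Patients are then approached in list order or random order.
- Word criterion 4 without reference to the trial's overview consultation.
- Record numbers listed, approached and consented, by arm.
- Where the three-month inclusion period allows, complete consent and baseline questionnaires before disclosure. A locked list reduces identification bias but leaves consent open to it; this step closes that route too.
- As a separate wording point, reconcile *Definition of complicated multimorbidity*, which presents the staff judgement as a looser definition for some patients, with *Inclusion criteria*, which requires all four criteria of everyone.

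The list, log and rewording are cheap. Recruitment training would have to precede the arm-specific content, so the single course is split or re-ordered and the first overview consultations start slightly later. The reworded criterion may slightly broaden who is listed. Consent and baseline before disclosure costs more, because it uses part of the inclusion period.

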### Exclusion criteria:

Patients who cannot speak Danish, cannot give informed consent, for example, people with dementia, or who have a life expectancy of less than 12 months will be excluded.

### Definition of complicated multimorbidity:

The patient has more than one of the 3 common chronic diseases (diabetes, chronic obstructive pulmonary, chronic heart conditions) [27], has been hospitalised, or visited an outpatient clinic due to their chronic diseases during the previous year [17], take at least five different prescription drugs assessed from the Shared Medicine Card recording (FMK, in Danish “Fælles Medicinkort”) in the general practice [28]. Lastly, some multimorbidity patients are more loosely defined by the GP or the nurse in the practice that recognise the patient as a “demanding” patient with complicated multimorbidity that will benefit from an overview consultation.

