## **Background**

The increasing prevalence of multimorbidity, defined as the coexistence of two or more chronic conditions in the same person [1], [2], is driven by the aging population and improved health technologies and represents a major challenge for healthcare systems. In the Capital Region of Denmark and Region Zealand, about 22% and 37% of the citizens aged 16 years and older suffer from multimorbidity [3], [4]. Around 10% of people with multimorbidity have complicated multimorbidity characterized by suffering from a symptom complex with several concomitant chronic conditions [5]. Researchers have proposed different definitions of complicated multimorbidity such as the severity of conditions, perception of illness, and more [6], [7]. Patients with complicated multimorbidity often have reduced health-related quality of life [8], [9], high treatment burden, polypharmacy, reduced ability to work, low employability, and increased mortality [5].

Healthcare systems are designed to take care of patients with single conditions. Unfortunately, the organisation according to specialities causes problems for the provision of integrated care for patients with multimorbidity. Thus, care pathways are often fragmented, with multiple appointments, more frequent hospital admissions, ambulatory visits, and use of other healthcare. The underlying causes for fragmented care are associated with the lack of a clear division of responsibilities and insufficient coordination between healthcare organisations. This is aggravated by non-integrated economic incentives between general practice, municipalities, and hospitals as well as by IT systems that are not always compatible and different care- and leadership cultures. Disease management programs (DMPs) have been developed to support integrated care but these may not be adequate for patients with multiple conditions and lowered self-care ability, and adhering to multiple DMPs may result in too much medication, conflicting treatments, an overload of appointments, and fragmented health care [10]. Also, providing care to patients with multimorbidity in practices where the rate of patients with multimorbidity is high seems to increase risk of burnout among general practitioners (GPs) [11].

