## *Setting*

The study will be carried out in Region Zealand and the Capital Region of Denmark, in general practices in three municipalities, in close collaboration with healthcare centers in the municipalities and hospital medical departments hospitals. The general practices should have a minimum of 4,500 patients registered to make sure that the number of patients with complicated multimorbidity reaches the needed number of 25 patients per practice. In addition, the practice needs to be able to include a care coordinator a few hours per week for five months. The municipalities were selected based on the rank of sociodemographic groups (III and IV, lowest) as the prevalence of patients with complicated multimorbidity is higher and the patients are sicker from their multimorbidity. Moreover, the possible benefits of the CIM2 model are expected to be larger in patients from municipalities of these sociodemographic groups.

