Further, since the extended overview consultation is a key element in the intervention, video recordings of conducted intervention consultations are gathered and analysed to evaluate if the consultation supports the relational competencies of the GPs needed to ensure that the patients concerns and priorities are articulated and taken into account. A combination of interactional linguistics [34] and a

psychological interpretative framework [35] is used to analyse the relational aspects of the interactions. The video recordings will furthermore be used for evaluation in the conduction of video-stimulated recall interviews (VSRI) [36]. These interviews will elucidate how elements of the model affect the GPs' ability to work with relational competence, to help reduce work burden and prevent burnout. The analysis conducted for this evaluation will consist of Conversation Analysis and a psychological interpretive framework [35].

To supplement the qualitative data on the delivery of the intervention, quantitative data will be generated from the REDCap data collecting program (e.g., number of consultations delivered, number of care plans prepared, and the extent of cross-sectorial communications).

Based on the overall analysis, a proposal is prepared for the possible adjustments of the CIM2 model before the national trial. Subsequently, the results (including any adjustment proposals) are communicated to relevant stakeholders, who are given the opportunity to comment on the results, which may give rise to further adjustment to the CIM2 model before the national trial.

*2) Assessing the acceptability and feasibility of the cluster RCT study design and procedures*

The acceptability and feasibility of the study's tools and procedures for randomisation, recruitment, and data collection will be assessed through qualitative interviews with health professionals and patients supplemented by quantitative data generated by the study (e.g., variations in the number of recruited patients and questionnaire response rates). Patient characteristics according to age, gender, chronic conditions, medication, and care plans will be presented to the general practitioners, nurse care managers, and specialists to validate whether the identified and recruited patients are the "right" patients in need of the CIM2 model and the inclusion criteria are relevant.

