where the variation of the random effect component  $Z$  reflects the ICC. Simulating the above model for 10.000 times per choice of the number of clinics in each group, with individually evaluated random loss to follow up, yields a power of 78%, 84% for 6 and 7 clinics in each group, respectively, based on a two-sided test at the level  $\alpha = 0.05$ . The uncertainty of these powers is found to be less than 1 percentage point, using the binomial formula. Thus, to obtain a power of 80% for detecting the specified difference  $\Delta$  from the random effects modeling, 7 clinics of 25 patients, i.e. 175 patients are needed in the intervention and control group.

The results from the pilot study will strengthen the validity of the estimates and clarify assumptions used in the power calculation. In particular, the results will clarify the need for implementing an ICC in the analysis of the main RCT, and if so, provide the power calculations with an estimated ICC value adapted to local conditions. Furthermore, the results from the pilot study will help to ascertain if 25 patients from each practice is a realistic number to include in the main RCT.

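### Does the definition of complicated multimorbidity open a second, looser route into the trial beside the four inclusion criteria?

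*Protocol*

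**What the plan says.** Two neighbouring sections of the protocol describe the trial population.

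- **Inclusion criteria.** "The study group is patients with complicated multimorbidity in general practice that fulfil the four inclusion criteria". The numbered items are: (1) more than one of three named chronic diseases; (2) a hospital stay or outpatient visit for those diseases in the past year; (3) five or more prescription drugs; (4) recognition by the GP or practice nurse as a demanding patient who would benefit from an overview consultation.
- **Definition of complicated multimorbidity.** This gives items 1 to 3 in the same order and nearly the same terms. It then closes with a sentence on recognition that begins "Lastly, some multimorbidity patients are more loosely defined by the GP or the nurse in the practice".

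Under Eligible patients, the protocol says who applies the rule: "The healthcare professionals in general practice identify eligible patients for the project".

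**The concern.** The closing sentence of the definition does not fit the list. A condition required of everyone cannot apply to only *some* patients, and an added requirement makes a group narrower, not looser. Taken literally, the sentence suggests either a separate way in for patients recognised by the clinician, or recognition as an optional feature.

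The inclusion list also relies on the defined term, both in its lead sentence and in criterion 4. The Background section notes that "Researchers have proposed different definitions of complicated multimorbidity", so a reader could turn to the definition to learn what the term means in this trial and meet the looser wording there.

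This is a pilot in which recruitment is itself under study. If practices worked to different rules, three outputs would be harder to interpret:

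- the check on whether those recruited are the right "patients in need of the CIM2 model and the inclusion criteria are relevant" (evaluation objective 2);
- the evidence meant to "help to ascertain if 25 patients from each practice is a realistic number to include in the main RCT" (evaluation objective 3);
- the local intraclass correlation, since between-practice differences in case mix could partly reflect the wording.

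These results feed the design of the national MM600 trial.

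**Working it through.** There is no stated figure to reproduce. The question is one of logic: can any reading of the definition change who is eligible?

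**Notation.** Let C1 to C4 be the four numbered criteria and D the definition of complicated multimorbidity. The lead sentence of the inclusion list requires the patient to have the condition and to fulfil all four criteria:

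Eligible = D and C1 and C2 and C3 and C4.

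**Readings of D.**

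| Reading of the definition | D | D combined with C1 to C4 |
|---|---|---|
| Recognition is a fourth joint element | C1 and C2 and C3 and C4 | C1 and C2 and C3 and C4 |
| Recognition is an alternative route | (C1 and C2 and C3) or C4 | C1 and C2 and C3 and C4 |
| Recognition applies to some patients only, so is not required | C1 and C2 and C3 | C1 and C2 and C3 and C4 |

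The eligible set is identical in every row. In general:

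1. *It cannot widen.* Combining any D with the four criteria gives a subset of those who meet all four. A patient who has only the clinician's recognition still fails C1, C2 or C3.
2. *It does not narrow.* A patient who meets all four criteria satisfies D in each of the three rows, so nobody on the list is shut out.

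**The term inside criterion 4.** Criterion 4 also mentions complicated multimorbidity. Putting any of the three versions of D there changes nothing, because C1 to C3 are separate numbered items that must still be met.

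**Other uses of the term.** The Setting section asks for at least 4,500 registered patients "to make sure that the number of patients with complicated multimorbidity reaches the needed number of 25 patients per practice". That is a condition on the practice and sets no rule for patients.

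**Scale.** The only arithmetic available is on design figures: 25/4,500 = 0.56% of a minimum-size list; one patient is 1/25 = 4% of a practice's sample and 1/350 = 0.29% of the trial. These show the weight of one misclassified patient. They do not say how many there would be, and the document gives nothing from which to estimate that.

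**Dependence of the plan's figures.** The preliminary power calculation uses 25 patients per clinic, a difference of 0.36, an intraclass correlation of 0.1, a total variation of 1 and 30% loss to follow-up. None of these is derived from the disputed sentence.

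**The case for a change.** The strongest case for acting is that logic on the page is not practice in the clinic. Busy staff identify the patients, they are not blinded, and one of the two texts in front of them is loose. Correcting it would take one sentence, and an enrolment checklist in REDCap, which the trial already uses, would show which criteria each patient met.

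Part of this stands. The sentence is poorly worded, and its *some* and *more loosely* do not fit a requirement placed on every patient. A kinder reading exists: *lastly* introduces the fourth item in the same order as the list, there is no *or*, and *loosely* may only describe how subjective that item is. But it is not a comfortable reading.

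The step from poor wording to uneven enrolment does not stand. It needs staff to recruit from a definition paragraph while disregarding a numbered list that is headed as the inclusion criteria and states that there are four. The training described under the CIM2 intervention elements covers how to recruit and include patients, and the protocol gives it to general practice staff without limiting it to one arm; the extra content for intervention practices concerns care delivery and collaboration.

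Departures would also be partly visible. Under evaluation objective 2, patients' chronic conditions and medication are shown to clinicians to judge whether the right people were recruited, and register data on conditions and medicine are used to compare the groups. This is detection after enrolment and would be incomplete, but it limits what could go unnoticed.

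A checklist by criterion is reasonable practice. It is optional, and the contradiction does not make it necessary.

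**Conclusion.** The two sections differ in wording, but the difference leaves the entry rule intact. All four criteria are required under each of the three readings of the definition, so there is no second route into the trial. This is a clerical slip that analysts and sites can resolve from the inclusion list itself. Matching the definition's last sentence to the list would be a courtesy to readers and would alter no stated figure, analysis or conclusion.

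The conclusion rests on two assumptions: that the numbered inclusion list is the operative rule, as its heading and explicit count of four indicate, and that recruitment training follows that list. If a looser route had in fact been intended, the inclusion list would be the text at odds with that intention, but nothing in the protocol says so. The size of any effect on recruitment counts or the intraclass correlation cannot be derived from the document.
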